The name, contact information, and study schedule for interested and enrolled participants will be kept in a separate database. The automated list of potential participants to whom informational letters will be sent will be maintained in a separate database as well. This identifiable information is maintained in order to contact and follow-up with interested potential participants or enrolled participants. No study data will be stored in these databases. All identifiable data will be stored on secure, password-protected servers located at the Madison VA and only study personnel will be granted access. All data that is not identifiable (forms collected after enrollment that are identified only by study number) is stored on a UW DoIT server with a copy of this data retained on a VA server.

Data will be maintained by the Madison, WI VAMC following the completion of the study.

Safety and Protection of Data Collected in Qualtrics

The research team will manage study data through Qualtrics. Qualtrics is an electronic data management system that will be used to capture, edit, manage, and export study data for analysis. Qualtrics is a HIPAA-secure survey tool obtained through licensing agreement with the University of Wisconsin System and promoted for research by DoIT. Subject identifiable information is restricted at multiple levels;

1. Access to the Qualtrics system is restricted to those that have been granted access by the software administrators. User access requires supervisor approval, completion of HIPAA and Human Subjects Protection training, and completion of role-based training in the Qualtrics system.
2. In addition, users' access is limited to protocols for which they have some responsibility of protocol, subject, or data management.
3. Within those protocols, the ability to view and modify data is restricted based on their role in the conduct of the research project (e.g. regulatory staff do not have the privilege to view subject identifiable information).

In addition, the technical components of this software are managed by the UW-Madison's Bioinformatics Computing Group (for server maintenance, software upgrades, etc.), and security and software support is provided by CTRI staff. CTRI staff are able to access subject information in order to help end users of the software program when questions arise.

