In addition to examining whether BA affects smoking outcomes (the “Intervention Hypothesis”: see Figure 1), a secondary objective of the proposed research is to examine the treatment effects of BA on PTSD symptoms and affective distress. Examining these treatment effects will also identify potential mediators of BA on smoking outcomes. Although this initial research is not powered for mediation analyses, such analyses may nevertheless suggest how BA works for smokers with PTSD and provide critical pilot data for future treatment process research. A secondary benefit is that the proposed work will produce additional data on BA as a treatment for PTSD. The following are hypothesized treatment effects of BA that may promote smoking cessation:

PTSD Treatment Effect. Consistent with prior research^{6,7,8,11,19}, we posit that BA will reduce overall PTSD symptom severity. Exploratory analyses will also examine the BA effects on each PTSD symptom cluster (re-experiencing, avoidance, emotional numbing, hyperarousal) to refine analyses of potential mediators. Self-report PTSD symptom severity will be measured at treatment visits and at each follow-up visit. In addition, a structured clinical assessment of PTSD (via the Clinical Administered PTSD Scale; CAPS) will occur at baseline and end-of-treatment.

Negative Affect Treatment Effect. BA has been shown to reduce depressed mood during smoking cessation⁹, and increased engagement in reinforcing activities is associated with decreased negative affect⁵¹. Thus, we posit that BA will decrease negative affect following quitting smoking. We will also explore the effects of BA on other tobacco withdrawal symptoms (e.g., craving) since negative affect may be causally linked with such symptoms. In addition, exploratory analyses will examine the influence of BA on depressed mood because depression often co-occurs with PTSD⁵⁹. Negative affect, depressed mood, and withdrawal symptoms will be assessed at every study visit and follow-up visit. A structured clinical assessment of current depression, in addition to PTSD, will occur at baseline and end-of-treatment.

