Positive Affect Treatment Effect. Evidence suggests that increasing the frequency of engagement in reinforcing activities elevates positive affect⁵¹. Therefore, we posit that BA will lead to increased global positive affect. In general, there is evidence that BA modulates reward functioning (i.e., approach toward rewarding events). Administration of BA results in functional

changes in brain structures that mediate both reward anticipation (incentive value) and reward feedback⁶⁰. It is unclear how BA's enhancement of the brain reward system maps onto actual behavior. It is possible that BA will also increase the sensitivity of the Behavioral Activation System (BAS), one of the major motivational systems associated with goal attainment and reward seeking. Thus, exploratory analyses will examine whether BA increases the sensitivity of the Behavioral Activation System. Positive affect and sensitivity of the Behavioral Activation System will be measured at every study visit (albeit, with only questionnaire measures).

Exploratory Mediation Analyses. Separate treatment effect hypotheses address whether BA, on top of a common smoking cessation base, affects PTSD symptoms, negative affect, and positive affect. Separate analyses will determine the relations of these latter variables with likelihood of smoking abstinence (the outcome hypotheses). We will conduct exploratory mediation analyses for variables that are influenced by BA and that also predict smoking outcomes. Although the proposed research is not powered for mediation, detecting treatment or outcome effects will provide relevant information about how BA works (or does not work), and how it can be improved. Finally, while not a mediational analysis, exploratory analyses will analyze the extent to which improvement in PTSD symptoms and affect in the ST+BA condition depends upon execution of behavioral assignments (e.g., engaging in reinforcing activities). This is an important test of the model by which BA is thought to work.

Significance

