Veterans with PTSD represent a large group of patients who would reap the known health benefits of stopping smoking⁶⁴ if the effectiveness of cessation treatment is improved. The VA has placed high priority on providing specialized care to approximately 560,217 veterans with PTSD⁶⁵. Stopping smoking would reduce the risk of tobacco-related cancer, cardiovascular, cerebrovascular, and respiratory diseases in those with PTSD²². In addition, the rapidly expanding number of veterans returning from deployment to Iraq and Afghanistan with comorbid nicotine dependence and PTSD⁶² suggests there will be an increasing demand for smoking cessation services and medical and psychiatric care from these veterans for years to come. A decline in smoking in veterans with PTSD would result in substantially lower smoking-related illness and death in this vulnerable clinical population. It would also dramatically reduce tobacco-related healthcare costs charged to the VA. The relevance of this research is further enhanced because the tested intervention targets both PTSD symptoms as well as smoking cessation. Finally, the relevance of the proposed work is underscored by the fact that BA is a brief and easily administered treatment that is readily accepted by veterans with PTSD^{8,11}. Thus, ST+BA could easily and readily be translated into VA clinical practice.

Research Design and Methods

Study Objective

The primary goal of the proposed research is to examine whether behavioral activation as an adjuvant to standard smoking cessation treatment (ST+BA) improves smoking cessation outcomes among veterans with PTSD relative to a comparably intense combination of standard smoking cessation treatment + health and smoking education (ST+HSE).

Specific Aims/Study Objectives

Primary Aim:

Aim 1: Compare the effects of behavioral activation (BA) and health and smoking education (HSE) on abstinence rates, when each is used as an adjuvant to standard smoking cessation treatment (ST+BA vs. ST+HSE).

Secondary Aims:

Aim 2: Compare the effects of behavioral activation (BA) and health and smoking education (HSE) on PTSD symptoms and affective distress when each is used as an adjuvant to standard smoking cessation treatment.

Aim 3: Identify potential mediators of the effects of BA on smoking cessation outcomes.

Design Overview

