In accordance with VA policy, in the case of reporting incidents, i.e. theft or loss of data or storage media, unauthorized access of sensitive data or storage devices or non-compliance with security controls, the Information Security Officer and Privacy Officer will be notified within one hour to determine an appropriate course of action.

Statistical Considerations

Power considerations

Estimated effect sizes for the primary treatment comparison and the power available to detect these effects with two-tailed tests are provided below for the total $N = 120$ participants with 25% attrition, using intent-to-treat approach. We computed power for the GLMM longitudinal analysis using a SAS macro developed by Dang and colleagues¹⁰⁸.

Specific Aim 1: [name] recent trial of BA for smoking cessation in smokers with symptoms of depression showed that 19% of smokers who received ST+BA were abstinent at 6-months post-quit, relative to those who received a contact-control smoking cessation treatment (0% abstinence rate at 6-months post-quit). For a treatment of this intensity (ST+BA), we believe that an improvement of at least 15% at 26-weeks post-quit would be sufficiently large to support additional research. For the current study, we predict that 6-month point prevalence abstinence rates will be 20% for ST+BA and approximately 5% for ST+HSE. We computed power for the GLMM longitudinal analysis using a SAS macro developed by Dang and colleagues¹⁰⁹ with the following parameters: $N=45$ per group; 5 time-points; drop-out rate of 0.25; 5% vs. 20% treatment effect over time; random effects variance=1; and within-subject correlation=0.6. Power for this scenario is 0.85. Even though power estimates have accounted for an estimated 25% attrition for a sample of $N=90$, we increased the sample size by 30 participants ($N=120$) to ensure that we have sufficient statistical power (which accounts for 25% attrition). Thus, the current study will have strong statistical power in the GLMM analyses.

Data and Record Keeping

Data elements will be collected and stored during the screening assessment and all visits and phone assessments. During the screening session, data resulting from structured clinical interviews assessing Axis I Disorders will be collected and stored. In addition, questionnaires measuring mood, medical history, smoking characteristics, craving, withdrawal symptoms, CO levels, behavioral activation, and demographic information will be collected and

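### Aim 3 estimates indirect effects only for variables that pass an undefined two-path screen in the same data, so the reported indirect effects are biased upward

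*Combined protocol and SAP*

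**What the plan says.** The rule is in the paragraph *Exploratory Mediation Analyses*, under *BA treats PTSD-specific smoking relapse risk factors*. The paragraph names three variables: PTSD symptoms, negative affect and positive affect. The effect of BA on each is tested, and then: "Separate analyses will determine the relations of these latter variables with likelihood of smoking abstinence (the outcome hypotheses". The next step is conditional: "We will conduct exploratory mediation analyses for variables that are influenced by BA and that also predict smoking outcomes".

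No significance level, adjustment for arm or estimation method is stated for either condition. Nothing says that estimates passing it will be treated as selected. *Power considerations* deals only with Aim 1.

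The plan is open about the limits: "Although the proposed research is not powered for mediation, detecting treatment or outcome effects will provide relevant information". It also states a use for the results: "such analyses may nevertheless suggest how BA works for smokers with PTSD and provide critical pilot data for future treatment process research". In *Specific Aims/Study Objectives* the secondary aim is worded modestly: "Identify potential mediators of the effects of BA on smoking cessation outcomes".

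Further exploratory treatment-effect analyses are planned on depressed mood, withdrawal and the Behavioral Activation Scale (BAS). Those on the PTSD clusters are meant to refine the search for mediators: "Exploratory analyses will also examine the BA effects on each PTSD symptom cluster".

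**The concern.** The indirect effect is the product of two estimates: the effect of BA on the mediator (path a) and the relation of the mediator to abstinence (path b). If the product is computed only when both estimates have already stood out in the same data, it is reported mainly when chance has pushed one or both upward. The fewer the abstainers, the noisier path b and the stronger this selection.

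A later team that uses the reported indirect effect to plan process research would then expect too much of the mechanism. For a variable that fails the screen, that team would have no indirect effect and no interval, so it could not tell a small effect from an imprecise one.

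**Working it through.** **Inputs from the protocol.** 26-week abstinence of 20% against 5%, two-tailed tests, 120 participants and 25% attrition (*Power considerations*). The sample size reproduces: 90/0.75 = 120. The two sizes used are therefore 45 per arm (after attrition) and 60 per arm (all randomised). The plan has no figure for Aim 3 to reproduce; its power of 0.85 belongs to Aim 1.

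**Assumptions.** A screen at p<0.05 on each path; path b adjusted for arm; a single binary outcome at 26 weeks; complete mediator data; BA effect d = 0.3, 0.5 or 0.8; odds ratio (OR) for abstinence per SD of mediator 1.5 or 2.0. None of these is in the documents.

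**Step 1: events.** 45 × 0.20 + 45 × 0.05 = 9 + 2.25 = 11.25 abstainers. 60 × 0.20 + 60 × 0.05 = 12 + 3 = 15.

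**Step 2: why selection bites, by hand.** Take 45 per arm, d = 0.3, OR 1.5.
- Path a: SE = √(2/45) = 0.211, so a passing estimate must exceed about 1.96 × 0.211 = 0.413, which is 0.413/0.3 = 1.38 times the truth.
- Path b: simulated power is 0.19, so true effect/SE ≈ 1.96 − 0.88 = 1.08, and a passing estimate must be about 1.96/1.08 = 1.81 times the truth.
- Product: roughly 1.38 × 1.81 = 2.5. Even the smallest passing indirect effect is about 2.5 times too large.

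With d = 0.5 and OR 2.0 the thresholds are 0.413/0.5 = 0.83 and, at power 0.49, 1.96/1.935 = 1.01. The product is 0.84, so selection is milder.

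**Step 3: simulation.** 4,000 trials per setting. Mediator = d × arm + N(0,1); logistic abstinence model calibrated to 5% and 20%; indirect effect = a × b on the log-odds scale. Ratios are estimate/truth, shown as mean (median).

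| Per arm | d | OR | Passes both | Unscreened | Screened |
|---|---|---|---|---|---|
| 45 | 0.3 | 1.5 | 0.06 | 1.08 (0.76) | 4.52 (4.06) |
| 45 | 0.3 | 2.0 | 0.14 | 1.10 (0.91) | 2.79 (2.54) |
| 45 | 0.5 | 1.5 | 0.13 | 1.09 (0.90) | 3.03 (2.80) |
| 45 | 0.5 | 2.0 | 0.32 | 1.09 (0.96) | 1.95 (1.79) |
| 45 | 0.8 | 1.5 | 0.19 | 1.08 (0.96) | 2.47 (2.31) |
| 45 | 0.8 | 2.0 | 0.47 | 1.10 (1.01) | 1.58 (1.47) |
| 60 | 0.3 | 1.5 | 0.10 | 1.06 (0.84) | 3.25 (3.01) |
| 60 | 0.3 | 2.0 | 0.22 | 1.06 (0.93) | 2.19 (1.98) |
| 60 | 0.5 | 1.5 | 0.21 | 1.06 (0.92) | 2.30 (2.14) |
| 60 | 0.5 | 2.0 | 0.48 | 1.07 (0.97) | 1.55 (1.45) |
| 60 | 0.8 | 1.5 | 0.28 | 1.08 (1.01) | 2.00 (1.89) |
| 60 | 0.8 | 2.0 | 0.60 | 1.06 (0.99) | 1.37 (1.27) |

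Two intermediate settings give screened medians at 45 and 60 per arm of 3.5 and 2.6 (d 0.3, OR 1.6), and 2.3 and 1.8 (d 0.4, OR 1.8).

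**Step 4: sensitivity.**
- Screening on a path b not adjusted for arm, in the same settings: screened medians 1.24 to 3.44 at 45 per arm and 1.10 to 2.50 at 60.
- A generous 88 per arm, to allow for repeated measures (a single-time comparison needs 86 per arm for 0.85 power): screened means 1.08 to 2.29 over d 0.3 to 1.19 and OR 1.5 to 2.5.
- d = 1.19, the protocol's only between-arm effect (a pilot of 8 people, against treatment as usual), with OR 2.5 and 60 per arm: 0.83 pass and the screened median is 1.11.

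**Step 5: does the screen cost detection?** At 45 per arm, the share of trials in which an unscreened interval for a × b excludes zero, against the share passing the screen: 0.04 against 0.06 (d 0.3, OR 1.5), 0.28 against 0.32 (d 0.5, OR 2.0), 0.46 against 0.47 (d 0.8, OR 2.0). They are nearly the same.

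**The case against.** The best defence is that this is a secondary analysis, labelled exploratory and admitted to be unpowered, whose aim is to identify candidates, not to size them. Both paths are analysed for the three named variables in any case, so none vanishes from the report. All of this is correct and limits the importance of the point. It does not remove the bias: the separate path results supply neither an indirect effect nor its interval, and the plan itself offers the mediation results as pilot data.

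Three stronger readings are tempting, but the documents do not support them.

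- *The screen discards most true mediators.* This depends on effect sizes and a threshold that the plan does not give. Over a wider grid (d 0.3 to 1.19, OR 1.5 to 2.5), fewer than half of true mediators pass in 10 of 12 settings at 45 per arm with an arm-adjusted path b, but in only 4 of 12 at 60 per arm without adjustment. Step 5 shows that the losses come mainly from low power: requiring both paths is close to a joint-significance test.
- *A long candidate list makes a false mediator likely.* The mediation paragraph names three variables, and the rule needs both paths. For a variable null on both, the chance of passing is about 0.05 × 0.05 = 0.0025. For three independent ones it is 1 − 0.9975³ = 0.7%. A variable that truly predicts abstinence needs only a false BA effect, which is at most a 5% chance each.
- *Failing the screen will be read as proof that BA does not work that way.* The sentence that invites this, "detecting treatment or outcome effects will provide relevant information about how BA works (or does not work", concerns what detected effects would show, and it opens by conceding the lack of power. The plan does not say how a non-detected path will be interpreted.

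**Conclusion.** The point holds in limited form. The screen is in the text, uses the trial's own data and has no stated criterion. Indirect effects reported only after passing it were biased upward in every setting tried.

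With p<0.05 screens and path b adjusted for arm, median inflation is about 2 to 3.5 times for d 0.3 to 0.4 (OR 1.6 to 2.0) and about 1.3 to 1.8 times for d 0.5 to 0.8 at OR 2.0. A weaker link to abstinence makes it worse: at OR 1.5 it is about 3.0 to 4.1 times for d 0.3 and 1.9 to 2.8 times for d 0.5 to 0.8. Very large effects bring it close to 1. Without the screen the mean ratio is about 1.1 or less.

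The size rests on the assumed threshold, effect sizes and single outcome time; the direction does not depend on the particular values tried. The primary aim is untouched. The change is worth making because the estimates are intended for reuse and the remedy costs little.

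**What to change.** Replace the conditional sentence with a fixed rule. For PTSD symptoms, negative affect and positive affect, report path a, path b adjusted for arm, and the indirect effect with a bootstrap or product-distribution 95% interval, whatever the significance of either path. State that a wide interval is inconclusive, not evidence against the mechanism.

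Indirect effects for PTSD clusters, withdrawal, depressed mood or BAS should be labelled exploratory. If any are screened, give the criterion and mark the estimates as selected.

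The rule should also say how the model is fitted if an arm has no abstainers. At 5% and 45 participants that has probability 0.95^45 = 0.10, and it would occur in some bootstrap samples too.

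The cost is a paragraph of analysis-plan text and a few more model fits, with no new data and no change to conduct. The reference list already includes works on product-distribution limits. The drawback is that some intervals will be wide: the change removes most of the inflation but does not add power.

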One hundred and twenty participants will be enrolled. For inclusion in the study, participants must: 1) report smoking an average of 6 or more cigarettes daily for at least six months; 2) report a desire to quit smoking; 3) meet criteria for *current* PTSD; 4) speak and read English; 5) agree to participate in the study; and 6) be \geq 18 years old.

Participants will be excluded from the study based on the following: 1) meeting criteria for psychotic or bipolar disorder; 2) psychoactive substance abuse or dependence (excluding nicotine dependence) within the past 6 months; 3) inability to give informed, voluntary, written consent to participate; 4) current use of any pharmacotherapy for smoking cessation not

provided by the researchers during the quit attempt; 5) use of non-cigarette tobacco or nicotine products as a primary form of tobacco/nicotine use; 6) being currently suicidal or homicidal, as assessed by VA suicide/homicide template questions administered to all veterans; 7) being medically unable to use the nicotine patch or nicotine gum/lozenge; 8) psychotropic medication changes within 2 months of study initiation and during active treatment; 9) current engagement in evidence-based therapies for PTSD or depression; 10) pregnant or trying to become pregnant; or 11) incarceration.

In addition, we will inform participants that, for research purposes, we prefer that they remain on the same psychotropic medication regimen throughout the trial. However, if it is necessary for a participant to alter treatment for his/her welfare, we will ask the participant to notify us immediately. Such participants will remain in the trial, but primary study analyses will be conducted with such participants excluded.

Any concerns regarding nicotine patch, gum, or lozenge use will be reviewed by the study clinician, who may interview patients should further information be required. All women of childbearing potential will be required to agree to use an approved method of birth control to prevent pregnancy during the period of nicotine replacement therapy (NRT) use. Participants with suicidal or homicidal ideation at screening will be referred for VA psychiatric care, and they will be excluded from the study. Study candidates who express imminent intent for harm to self or others at any point in the study will be referred for VA emergency care.

Assessments

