Primary Care PTSD Screen (PC-PTSD). The PC-PTSD⁸⁸ is a validated, four-item measure of PTSD with yes-no response options used by the Department of Defense Post-Deployment Health Assessment Program to identify veterans with possible PTSD. Two yes answers have been shown to yield sensitivity of .96 and specificity of .78⁸⁹. Study candidates who yield one or more yes answers on the PC-PTSD at the phone screen will be further assessed by an in-person diagnostic interview.

Clinician Administered PTSD Scale (CAPS). The CAPS⁹⁰ will be used to determine PTSD diagnostic status and severity. It will be administered at baseline and at the end of treatment (V10; see Table 1). The CAPS is a widely used and validated clinician interview for the assessment of PTSD. PTSD diagnosis on the CAPS is based on meeting the symptom criteria as defined in the most recent version of the Diagnostic and Statistical Manual of Mental Disorders (DSM). The CAPS shows strong internal validity⁹⁰. In addition, time since trauma, number of traumatic exposures, type of trauma, and time since original PTSD diagnosis will be assessed to aid in identifying factors that may be associated with treatment outcomes.

Structured Clinical Interview for DSM Axis I Disorders (SCID-I). The SCID⁹¹ is a widely used structured interview that assesses psychiatric disorders. The SCID-I has been shown to have very good reliability and validity⁹². The SCID-I will be administered at baseline, and only the depression module of the SCID-I will administered at the end of treatment (V10). If depression is noted in the SCID and participants are not already receiving clinical care, they will be referred to a clinical care provider. Questions pertaining to illicit drug use will be asked, but not recorded to protect participant privacy.

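### Randomised participants who change psychotropic treatment are dropped from the primary analyses, although the plan calls the primary comparison intent-to-treat on all 120

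*Combined protocol and SAP*

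**What the plan says.** Four parts of the combined protocol and SAP bear on this.

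- **Inclusion and Exclusion Criteria, paragraph after the exclusions.** Participants are told that "we prefer that they remain on the same psychotropic medication regimen throughout the trial". The next sentence covers unavoidable changes: "if it is necessary for a participant to alter treatment for his/her welfare, we will ask the participant to notify us immediately". The consequence follows: "Such participants will remain in the trial, but primary study analyses will be conducted with such participants excluded".
- **Same section, exclusion 8.** The list of grounds for exclusion from the study includes "psychotropic medication changes within 2 months of study initiation and during active treatment".
- **Statistical Considerations, Power considerations.** Effect sizes and power for the primary treatment comparison are given for a total of 120 "participants with 25% attrition, using intent-to-treat approach". This is the only mention of intent-to-treat, and there is no separate section defining analysis sets.
- **Study Objective, Aim 1 and Smoking Status Assessments.** The primary aim compares abstinence rates between ST+BA and ST+HSE, with 7-day point prevalence abstinence as the main outcome.

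No passage defines a modified intent-to-treat set, says which statement governs, or labels either analysis as a sensitivity analysis.

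**The concern.** The trigger for exclusion arises after randomisation, and the document itself gives reasons why it could be linked to arm and to outcome. On PTSD symptoms, "we posit that BA will reduce overall PTSD symptom severity"; negative affect is also expected to fall. The background sections argue that affective distress drives relapse. The symptoms that could prompt a medication change are therefore ones the treatment is meant to alter and ones thought to predict smoking. A study procedure may add to this. In the SCID-I description, "If depression is noted in the SCID and participants are not already receiving clinical care, they will be referred to a clinical care provider", and the depression module is repeated at V10, before the week-26 outcome.

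If the primary set is selected on such an event, Aim 1 no longer compares the groups as randomised, and part of any difference in abstinence may reflect who was removed. Two analysts could each follow the document and report different primary results.

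The excluded set is also poorly defined. Finding it relies on participants telling staff. The window is the whole trial in one sentence and active treatment in exclusion 8. Exclusion 8 reads as grounds for leaving the study, while the following paragraph keeps these people in it.

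**Working it through.** **1. The plan's own figures.** The step from 90 to 120 reproduces: 90/(1 - 0.25) = 120. The stated power of 0.85 (45 per group, 5 time points, 5% v 20%, drop-out 0.25, random-effects variance 1, correlation 0.6) could be neither confirmed nor refuted, because the time trend and covariance structure are not fully given. With two-sided alpha 0.05 assumed, approximations at 45 per group give 0.58 for a single time point and 0.62 to 0.81 for five visits. The point made here does not depend on that figure.

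**2. Effect of the exclusion on the estimate.** In one arm let

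- p = true abstinence,
- ca = share of abstainers who change medication,
- cs = share of continuing smokers who change medication.

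The abstinence rate among those still analysed is

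p(1 - ca) / [p(1 - ca) + (1 - p)(1 - cs)].

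The planned rates of 20% and 5% come from Power considerations. The change rates are assumptions: ca of 5, 10, 15 or 20%, the same in both arms; cs of 10, 15, 20, 25 or 30%, free to differ by arm.

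*No true effect, p = 12.5% in both arms (midpoint of 5% and 20%).* With ca = 10%:

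- ST+HSE, cs = 30%: 0.125 × 0.90 / (0.125 × 0.90 + 0.875 × 0.70) = 0.1125/0.725 = 15.5%
- ST+BA, cs = 15%: 0.1125 / (0.1125 + 0.875 × 0.85) = 0.1125/0.85625 = 13.1%
- Spurious difference: -2.4 points against ST+BA; +2.4 if the arms are swapped.

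Over the whole grid the range is -3.1 to +3.1 points, with extremes at ca = 5% and cs = 10% v 30%. It is zero whenever cs is equal by arm. The range depends on the null rate chosen: ±1.4 points at p = 5% and ±4.5 at p = 20%.

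*Planned effect, 20% v 5% (true difference 15.0 points).*

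| ca | cs ST+BA | cs ST+HSE | ST+BA | ST+HSE | Difference |
|---|---|---|---|---|---|
| 10% | 15% | 30% | 20.9% | 6.3% | 14.6 |
| 10% | 30% | 15% | 24.3% | 5.3% | 19.0 |
| 10% | 20% | 20% | 22.0% | 5.6% | 16.4 |
| 20% | 10% | 30% | 18.2% | 5.7% | 12.5 (lowest) |
| 5% | 30% | 10% | 25.3% | 5.3% | 20.1 (highest) |

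The third row shows that, when there is a real effect, the estimate moves even if smokers change at the same rate in both arms.

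**3. Effect on the false-positive rate.** A Wald approximation with 60 per arm before exclusions and alpha 0.05 gives, at the worst grid point, about 0.060 for p = 5% and 0.072 for p = 12.5%. The 15% v 30% example at p = 12.5% gives about 0.062. A harsher model, in which everyone excluded is a smoker and 10% of one arm and 30% of the other are removed, gives ±4.0 points and about 0.082 at p = 12.5%.

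**4. Precision.** Excluding a share f of the 120 inflates standard errors by 1/√(1 - f) - 1:

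- f = 10%: 108 left, about 5%
- f = 20%: 96 left, about 12%
- f = 25%: 90 left, about 15%

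The analysed number falls below the 90 used for the power figure only if more than 25% are excluded.

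**The case against.** The best defence is that the intent-to-treat phrase appears once, in the power section, and may describe only how drop-outs are counted there; the exclusion sentence would then be the sole explicit rule. That reading removes the contradiction but leaves a post-randomisation exclusion as the primary analysis, which is the worse outcome.

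Several narrower objections do stand.

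- **Precision is a minor issue.** Drop-out of 0.25 is already an input to the 0.85 power at 45 per group, so on the plan's own figures the 30 added participants are slack that could absorb exclusions of up to 25%.
- **The size is assumed throughout.** The 12.5% null is a chosen midpoint. At the plan's own control rate of 5% the spurious difference is at most 1.4 points, and the extremes need a threefold difference in smokers' change rates between arms, which no passage supports.
- **The SCID referral is weak support.** It also applies at baseline, a referral is not a medication change, and V10 follows the last therapy session, so it matters only if the window is the whole trial.
- **The assessment table settles little.** It shows no item for medication changes after baseline, but it also omits the automated telephone assessments, so a missing row does not prove that changes go unrecorded.

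The rule presumably aims to avoid confounding by new psychotropic medication; bupropion use is, after all, a randomisation factor. The aim is reasonable, but randomisation already balances the arms in expectation, and selecting on a later event can undo that. A sensitivity analysis serves the aim.

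**Conclusion.** The concern holds and should be corrected before the primary analysis. As written, the plan removes randomised, retained participants from the primary comparison because of a post-randomisation event, and this conflicts with its only statement of analysis principle. Bias in Aim 1 is possible in either direction; the document does not show that it is large. Under the assumed change rates it reaches about 3 points either way with 12.5% abstinent in both arms and no true effect, and shifts the planned 15-point difference by between -2.5 and +5.1 points. These figures illustrate scale and are not forecasts. The case rests on bias and on an undefined primary set, with lost precision secondary.

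**What to change.** Replace the exclusion sentence with wording such as: *Such participants remain in the trial and are included in the primary intent-to-treat analysis as randomised; an analysis excluding them is a labelled sensitivity analysis, with counts and reasons reported by arm.* State whether the same holds for the Aim 2 analyses, since the present sentence names only the primary ones. Reconcile exclusion 8 with the paragraph that follows it, on both the window and whether a change means leaving the study. This concerns the analysis set only, not how medication is managed.

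The cost is close to nil. The primary analysis needs no new data. The sensitivity analysis needs a record of whether and why a change occurred, which can be asked at existing contacts instead of relying on participants to report it.
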